1.1. Title

Comparing the effects of three different dressings on the cutaneous response to pressure and shear of sacral skin: an exploratory crossover study.

1.2. Trial registration

To be done after approval by the Ethics Committee at clinicaltrials.gov.

1.3. Protocol version

Version 1

1.4. Financial support

Mölnlycke Health Care AB
[name]
[name]
Sweden

2.1 Background and Rationale

Pressure ulcers (PUs), also called pressure injuries, are severe and unwanted cutaneous lesions and subcutaneous wounds caused by prolonged skin and underlying soft tissue deformation. In the supine position they predominantly occur near to bony prominences such as heels and the sacrum. The cornerstone of PU prevention is repositioning, early mobilization and the use of special support surfaces (National Pressure Ulcer Advisory Panel (NPUAP), European Pressure Ulcer Advisory Panel (EPUAP), Pan Pacific Pressure Injury Alliance (PPPIA) 2014).

In addition, empirical evidence suggests that the application of preventive dressings on PU predilection sites helps to prevent PU development (Clark et al. 2014). This is supported by results of a number of recent clinical trials (e.g. Santamaria et al. 2015, Kalowes et al. 2016, Forni et al. 2018) and is now also recommended in the latest Pressure Ulcer Prevention and Treatment Guideline (NPUAP, EPUAP, PPPIA 2014). The mode of action of PU preventive dressings includes mechanical cushioning and the reduction of shear loads within soft tissues and the reduction of the coefficient of friction between the dressing and the support surface (Call et al. 2015, Levy et al. 2015, 2017).

Many different dressings are on the market and the dressing performance is related to its material and structure. Results of *in vitro*, computer modelling, and *in vivo* studies indicate different effects on the skin microclimate, pressure reduction, and maybe also on clinical outcomes (e.g. Call et al. 2013, Dutra et al. 2015, Matsuzaki et al. 2015). However, results of laboratory or computer modelling studies are not automatically transferable to real-life situations. In addition, there are no high quality clinical trials with a direct head-to-head comparison of the most important competitors on the market. Therefore, it is not appropriate to generalize clinical study results of one dressing type to another (Gefen et al. 2016).

Next to the 'hard' clinical outcome 'PU development' there are a number of alternative biomarkers and parameters to characterize the response of the skin to prolonged loading and deformation. According to Bader and Worsley (2018) they may be classified into four categories: (1) 'Monitoring of the interface' (including interface pressure mapping, shear, friction and microclimate measurement); (2) 'Biophysical skin sensing' (skin measurements); (3) 'Biomarkers indicative of early skin damage' (for example cytokines, chemokines, lactate on the skin surface, blood markers such as CRP); (4) 'Medical imaging' (including MRI, CT, ultrasound, colour measurements). Skin functional parameters such as erythema or stratum corneum hydration and structural parameters, like structural stiffness, have been successfully used in PU prevention research (Dobos et al. 2015, Kottner et al. 2015). These parameters are able to discriminate effects of different loading intensities and to measure PU preventive device performance (Tomova-Simitchieva et al. 2017). Recently it also could be

shown that there are associations between structural and functional skin changes at the heel and sacral area during loading (Pfannes et al. 2018).

(Subclinical) injuries to the stratum corneum stimulate the production of inflammatory cytokines. In clinical PU research, it has been shown that levels of IL-1alpha are also useful to measure the inflammatory response of the skin due to mechanical deformation. It was demonstrated that the increase of cytokines is related to mechanical loading intensity (De Wert et al. 2016, Bader, Worsley 2018) and thus are suitable biomarkers to measure early skin response due to deformation.

Recently, Mölnlycke Healthcare sponsored a study to investigate the effects of pressure ulcer preventive dressings on loaded and unloaded skin. Between July and October 2016 n = 8 healthy males (mean age 28 years) were included into an exploratory cross-over trial to explore the effects of Mepilex® Border Sacrum and Heel on the sacral and heel skin with and without loading (CRC-SP-A-26). Main results were that the dressings have an occlusive effect in terms of accumulation of heat and humidity, but this was not very different to loaded skin without dressings. This increase of stratum corneum and epidermal hydration softened the skin and contributed to changes of skin topography. Finally, results indicate that loading increased the inflammatory cytokine IL-1alpha and that this increase seemed to be slightly lower when a dressing was applied. This may indicate that the dressing may reduce the inflammatory response. The detailed results are reported in the full study report version 2, December 2016.

Overall, the study results indicate that cutaneous structure and function parameters can characterize the response of heel and sacral skin due to loading and that it is possible to measure a particular dressing effect. However, the sample size was small, the loading duration of 2.5 hours was short, shear forces were reduced to a minimum, and the sample was not representative for patients at PU risk. Therefore, there is a need to repeat this study using a more relevant target group such as aged females, to increase the mechanical loading in terms of pressure and shear, and to compare directly different dressing types.

2.2 Aims

The overall aim of this study is to measure the effects of Mepilex® Border Sacrum on the skin structure and function during mechanical loading compared to (1) no dressing, (2) ALLEVYN Life Sacrum and (3) Optifoam® Gentle Liquitrap Sacrum.

The following objectives are determined:

(1) To measure the changes of skin temperature, stratum corneum hydration, erythema and skin roughness, (2) to evaluate clinical signs of pain and erythema and (3) to determine IL-1alpha and total protein of the sacral skin before loading (baseline) and after three and a

half hours loading with or without application of a dressing (Mepilex® border, ALLEVYN Life Sacrum, Optifoam® Gentle Liquitrap Sacrum).

3. Methods: Participants, interventions, and outcomes

3.1 Study design

This study is an investigator initiated explorative randomized cross-over trial using intraindividual comparisons. In total four interventions will be compared at the sacral skin (Table 1).

3.2 Study setting

The study will be conducted at the Clinical Research Center for Hair and Skin Science (CRC) at the Department of Dermatology and Allergy, Charité – Universitätsmedizin Berlin.

3.3 Eligibility criteria

Inclusion criteria

- Healthy female volunteers
- 65 to 80 years
- Body Mass Index 18.5 to 29.9 kg/m²
- Non-smoker of at least one year (including electronic-cigarettes)
- Informed consent
- Being free of any clinical dermatosis in the investigational area
- Intact sacral skin without scars
- Skin phototype I, II, or III (according to Fitzpatrick)
- No regular use of leave-on products on the sacral skin
- Willing and able to fulfil the study requirements

Exclusion criteria

- Disability to maintain in supine or prone position
- Acute diseases
- Known hyper-sensibility or allergy to the study product or any of its ingredients
- Extensive UV exposure 4 weeks before study inclusion
- Use of topical treatment on the investigational areas or systemic treatment within the 4 past weeks (topical hyaluronan, anti-inflammatory drugs, corticoids, retinoids, NSIDS etc.) that would interfere with assessment and/or investigational treatments
- Medical history of skin cancer
- History of established Diabetes mellitus, cardiac or renal insufficiency, COPD

- Chronic inflammatory skin disorders such as atopic dermatitis, psoriasis, lichen planus
- Participation in another study 4 weeks prior to study start

3.4 Study procedures and interventions

Volunteers will come to the study centre for four visits. In between, there are at least 3 weeks to prevent possible carry over effects. Therefore, the entire duration of one subject will be at least 9 weeks. The duration of one study visit per subject is approximately 5 hours. After four visits, each volunteer will have received each intervention once (A, B, C and D, see Table 1).

Table 1. Experimental interventions for the sacral skin

Intervention	Dressing
A	None
B	Mepilex® Border Sacrum
C	ALLEVYN Life Sacrum
D	Optifoam® Gentle Sacrum

After giving informed consent, subjects will lie down in supine position on a standard hospital mattress for a maximum of 10 minutes. Then subjects will turn around into prone position. Two fields of equal size (each 2cm x 2.5cm) will be marked with a skin pen, one for the baseline and one for the follow-up measurements. If an erythema has occurred at the sacral area during the 10 minutes in supine position, the investigational site will be marked within the reddened skin area. In case of no erythema, the test area will be identified by feeling the most protuberant point at sacrum. After marking the measurement area the subjects will acclimatize under standardized room temperature and humidity conditions (22±2°C, 40 to 60% rel. humidity) for 30 minutes with having the sacral skin uncovered. Subjects may lay (on the side) or sit during this period but must make sure that the investigational area is uncovered. After that, subjects will move into prone position and the following baseline measurements will be conducted according to CRC standard operating procedures (SOPs):

- (1) Measurement of skin surface temperature
- (2) Measurement of SC hydration (SCH)
- (3) Measurement of Erythema index (EI)
- (4) Visioscan images to measure Rz, Ra
- (5) Cyanoacrylate skin surface stripping (CSSS), to determine IL-1alpha and total protein of the sacral skin.

In addition to the instrumental measurements, erythema and pain will be evaluated clinically.

The measures of skin surface temperature, SCH and EI will be performed three times per measuring round. Two duplicate Visioscan images will be taken. CSSS will be performed at the end.

After the baseline measurements a randomization envelope will be opened to allocate the subject to one of the intervention groups A, B, C or D (see Table 1). The dressings (B, C, D) will be applied or the skin will be left uncovered (A), followed by a 3.5 hours loading period. The subject will lie in supine position on a standard hospital mattress. Every 30 minutes the head of the bed will be elevated to 45° for five minutes. During these five minutes, the participants will be instructed to bend their knees and to drag the feet repeatedly forth and back 10 times. Then the head of bed will be moved back again and the subjects can relax. The whole exercise will be done six times, after 0.5, 1, 1.5, 2, 2.5 and 3 hours.

After 3.5 hours loading time in supine position the subjects will move into prone position. In case of interventions B, C or D the dressings will be removed. Then all skin measurements and CSSS will be conducted again. After the end of the measurements and procedures, subjects will leave the study site. They will come back for another three times completing the remaining interventions.

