5.2 Statistical methods

Demographic characteristics will be described using numbers, proportions, means and standard deviations. Metric outcomes will be described using mean and spread parameters per intervention and time point. Baseline and follow-up parameters will be compared descriptively.

6 Methods: monitoring

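### The baseline-to-follow-up change, the only comparison section 5.2 names, mixes load with contact or cover and lost acclimatisation, so it cannot by itself be read as the response to pressure and shear; the dressing comparison survives.

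*Combined protocol and SAP*

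**What the plan says.** The title describes a study of dressing effects on "the cutaneous response to pressure and shear of sacral skin". Section 2.2 frames the objectives as changes between a reading before loading and one after three and a half hours of loading, with or without a dressing.

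Section 3.4 fixes the state of the skin at each reading:

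- **Before baseline.** First, "subjects will lie down in supine position on a standard hospital mattress for a maximum of 10 minutes". The fields are then marked and the woman acclimatises in controlled room air (22±2°C, 40 to 60% relative humidity) "for 30 minutes with having the sacral skin uncovered".
- **Before follow-up.** "The dressings (B, C, D) will be applied or the skin will be left uncovered (A), followed by a 3.5 hours loading period". She lies supine on the mattress in every intervention, then turns prone and any dressing is taken off. "Then all skin measurements and CSSS will be conducted again".

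No second acclimatisation and no waiting interval is stated before follow-up. Of the two marked fields, one serves baseline and the other follow-up; neither is an unloaded control. Table 1 lists four interventions that differ only in the dressing.

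Section 5.2 describes metric outcomes per intervention and time point and then names a single comparison: "Baseline and follow-up parameters will be compared descriptively". It names no contrast between interventions.

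**The concern.** Between the two readings several things change together: the skin goes from equilibrated in room air to enclosed against a mattress or under a dressing, posture differs, hours pass, and load is applied. A rise in temperature or hydration from baseline to follow-up could come from any of these.

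The background in section 2.1 gives grounds for taking this seriously. The sponsor's earlier study reported that "the dressings have an occlusive effect in terms of accumulation of heat and humidity", that loaded skin without dressings was similar in this respect, and that the added hydration softened the skin and altered its topography. Those findings bear on skin temperature, SCH and the roughness parameters. The earlier study also examined dressings "on the sacral and heel skin with and without loading"; the present design has no unloaded condition.

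At stake is the interpretation. Under this title, a before-after table is easily read as showing what pressure and shear did to the skin, and the design cannot isolate that.

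**Working it through.** The plan gives no power, variance or effect-size figure for this point, so there is no stated number to reproduce. Two checks apply.

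**1. What the four conditions can estimate.** Inputs: Table 1 (A none, B Mepilex, C ALLEVYN, D Optifoam) and the loading procedure in section 3.4, which is the same for all four. Let L be the effect of load, K the joint effect of contact or cover, lost equilibration, posture and time common to all interventions, and d the extra effect of each dressing. The expected change from baseline is then:

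- A: L + K
- B: L + K + d_B
- C: L + K + d_C
- D: L + K + d_D

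That is four equations in five unknowns, with rank 4 of 5. Adding any constant to L and subtracting it from K leaves all four lines unchanged, so neither L nor K is estimable; only L + K is. More subjects would not alter this.

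The differences between interventions are estimable:

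- B−A = d_B
- B−C = d_B − d_C
- B−D = d_B − d_D

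L + K drops out of each, because acclimatisation, loading and timing are the same in every intervention.

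Now split each dressing term into occlusion (o) and a changed response to load (m), so that d_B = o_B + m_B and likewise for C and D. There are then 2 + 3 + 3 = 8 terms and still four conditions, with rank 4 of 8, and m_B is not estimable. B−A therefore gives o_B + m_B, and B−C and B−D contain the corresponding differences between dressings.

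**2. Whether an unstated second acclimatisation is likely.** Inputs from section 3.4: up to 10 minutes supine, 30 minutes uncovered, 3.5 × 60 = 210 minutes of loading, and a visit of about 5 × 60 = 300 minutes.

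- Fixed time: 10 + 30 + 210 = 250 minutes
- Left for marking and two measuring rounds: 300 − 250 = 50 minutes
- Left if another 30 minutes were added: 50 − 30 = 20 minutes

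The visit length gives no sign of a second acclimatisation. It does not rule one out, and the SOPs that section 3.4 refers to are not in the documents.

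**What separating the parts would take.** One unloaded, covered condition without a dressing raises the rank to 5 of 5 and makes L estimable. As an extra visit it means five visits and at least 4 × 3 = 12 weeks instead of 3 × 3 = 9. Separating occlusion from altered load response for every dressing needs unloaded counterparts of all four conditions (rank 8 of 8). As separate visits that is eight visits and at least 7 × 3 = 21 weeks.

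**The case against.** The strongest reply is that the trial exists to compare dressings. Section 2.2 sets Mepilex against no dressing and two competitors during loading, section 3.1 says four interventions are compared, and the shared shift cancels in those contrasts. This stands. A reader might infer that the head-to-head aim is compromised; the documents do not support that. What remains is that section 5.2 does not name those contrasts.

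Second, no passage says the change will be credited to load alone; section 5.2 promises only description. That also stands. The risk lies in how an unqualified before-after result would be read under this title.

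Third, lying on a mattress necessarily covers the sacrum, and section 2.1 lists microclimate beside pressure and shear as part of monitoring the interface. A combined effect is thus a legitimate quantity to report, provided it is named as one. Intervention A is called uncovered in the sense of having no dressing; its sacrum is still against the mattress.

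Two further inferences go too far. Section 2.1 does not show that cover alone moves the readings as much as loading does: its sentence compares dressings with loaded bare skin and does not say whether the dressed skin was loaded. Nor does the cover argument extend to every outcome. For erythema and IL-1alpha the documents report no cover effect, and section 2.1 says that loading raised IL-1alpha.

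Finally, this is an exploratory study of 12 women with no primary outcome and no hypothesis test. That lowers the weight of the point but does not make the two components separable.

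**Conclusion.** The point holds in a limited form. The within-intervention change estimates load together with contact or cover, lost equilibration, posture and time, and cannot by itself be presented as the response to pressure and shear. For temperature, SCH and roughness the protocol's own background documents a competing cause. For erythema and IL-1alpha the gap is only the absence of an unloaded reference.

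No size can be put on the share due to load: the documents give no figure for either part, and any percentage would rest on invented values.

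The conclusion assumes that follow-up is read without re-acclimatisation, which is inferred from the absence of any stated interval. The cancellation between interventions assumes additive effects and the same procedure at each visit. B−A remains valid as the overall effect of applying Mepilex under loading, but does not show how much of it is occlusion and how much a changed response to load.

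**What to change.** Amend section 5.2 in three respects:

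1. Make the dressing comparison the within-subject difference between interventions (B−A, B−C, B−D) in change from baseline under identical loading, reported descriptively with a measure of spread or a confidence interval.
2. Report the change within each intervention as the combined effect of loading and contact or cover, not as the effect of pressure and shear alone.
3. State that B−A combines the dressing's occlusion with any change in the response to load.

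This uses data the trial already collects and adds no procedure or visit. The cost is a few sentences and a narrower claim: the trial would report how dressings differ under loading, without isolating what load does.

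A second 30-minute uncovered period before follow-up is not a full remedy. It leaves the missing unloaded reference in place, and section 6.2 treats erythema lasting more than 30 minutes as persisting, so shorter-lived redness could fade before it is read.

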3.6 Variables and outcomes

Due to the explorative nature of this study, no distinction between primary, secondary or other variables is made (Table 3).

Table 3. Variables and outcomes

Name	Method and metric
Skin phototype	
 • Classification according to Fitzpatrick (nominal)
Height	
 • Measurements in the CRC • m (metric)
Weight	
 • Measurements in the CRC • kg (metric)
Age	
 • Checking by looking at the ID card • metric
Sacral pain	
 • Subjects' self-report • Pain (yes/no) (nominal) • Time to pain reporting in minutes (metric)
Erythema	
 • Visual inspection • VAS (metric)
Skin surface temperature	
 • Skin thermometer based in infrared technique (Courage and Khazaka Electronic GmbH) • °C (metric)
SCH	
 • Noninvasive instrumental measure using the Corneometer CM 825 (Courage and Khazaka Electronic GmbH) • Arbitrary units, A.U. (metric)
EI	
 • Noninvasive instrumental measure using the Mexameter MX18 (Courage and Khazaka Electronic GmbH) • Arbitrary units, A.U. (metric)
Rz, Ra, Rmax	
 • Visioscan VC 98 (Courage and Khazaka Electronic GmbH) • µm (metric)
Cytokines	
 • Cyanoacrylate skin surface stripping (CSSS) (or another sampling method) • IL-1, total protein in pg/µg • ELISA

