6.2 Harms

Harms, like pain, persisting erythema lasting for more than 30 minutes or possible irritant reactions, which occur immediately or after loading, will be documented as an adverse event.

Within this trial the following definitions of adverse events will be used:

Device Deficiency (DD)

Inadequacy of a medical device with respect to its identity, quality, durability, reliability, safety or performance.

Note: Device Deficiencies include malfunctions, use errors, and inadequate labelling. All Device Deficiencies that could have led to a Serious Adverse Device Effect shall be reported in accordance with Serious Adverse Event reporting procedures.

Adverse Event (AE)

Any untoward medical occurrence, unintended disease or injury, or untoward clinical signs (including abnormal laboratory findings) in subjects, users or other persons, whether or not related to the investigational medical device.

Note: This definition includes events related to the investigational medical device or the comparator. This definition includes events related to the procedures involved. For users or other persons, this definition is restricted to events related to investigational medical devices.

Adverse Device Effect (ADE)

Adverse Event related to the use of an investigational medical device

Note: This definition includes adverse events resulting from insufficient or inadequate instructions for use, deployment, installation, implantation, or operation, or any malfunction of the investigational medical device. This definition includes any event resulting from use error or from intentional misuse of the investigational medical device.

Serious Adverse Event (SAE)

Adverse Event that:

- i. leads to death;
- ii. leads to a serious deterioration in the health of the subject, that either resulted in;
 - a. a life-threatening illness or injury, or
 - b. a permanent impairment of a body structure or a body function; or
 - c. prolonged hospitalization; or,
 - d. medical or surgical intervention to prevent life-threatening illness or injury or permanent impairment to a body structure or a body function; or

Serious Adverse Device Effect (SADE)

Adverse Device Effect that has resulted in any of the consequences characteristic of a Serious Adverse Event.

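### Time to pain has no rule for women still pain-free when loading ends at 210 minutes; read literally, its mean covers only women who reported pain and can mislead about a dressing

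*Combined protocol and SAP*

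**What the plan says.** Section 3.6, Table 3, gives sacral pain by self-report two entries: "Pain (yes/no) (nominal" and "Time to pain reporting in minutes (metric". The same section states that "no distinction between primary, secondary or other variables is made".

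Section 3.4 sets the loading period and its end: "After 3.5 hours loading time in supine position the subjects will move into prone position". It also says: "In addition to the instrumental measurements, erythema and pain will be evaluated clinically".

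Section 5.2 has three sentences. The first reads "Demographic characteristics will be described using numbers, proportions, means and standard deviations". The second reads "Metric outcomes will be described using mean and spread parameters per intervention and time point". The third says that baseline and follow-up values are compared descriptively. None mentions censoring, a value for a woman without pain, or a denominator for the pain times.

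Section 6.2 includes pain among the harms to be documented as adverse events: "Harms, like pain, persisting erythema lasting for more than 30 minutes or possible irritant reactions".

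**The concern.** A time to pain report exists only for a woman who reports pain. For the others, all that is known is that the time exceeds the loading period, so they are right-censored at 210 minutes. The plan labels the variable metric and has one rule for metric outcomes, a mean with a measure of spread. Applied as written, that rule averages the times that exist and drops the pain-free women.

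That average compares different women under different interventions. A dressing that prevents pain removes women from its own average, and the result then depends on which women are removed. If those spared would have reported late, the early reporters remain and the dressing looks worse. If those spared would have reported early, the dressing looks better than it is. With no tests and no outcome hierarchy, the descriptive table is the result, so a misleading row in it has nothing to correct it except the pain counts. Section 5.2 does not require those beside the times.

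**Working it through.** **Inputs from the documents.** Loading lasts 3.5 h × 60 = 210 minutes (3.4). Twelve women each receive all four interventions (3.4, 3.7). The plan gives no pain rate, onset time or effect size, so there is no figure of its own to reproduce, and everything below about pain is assumed.

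**Two summaries compared.**
- Reporter-only mean = sum of reported times ÷ number reporting pain.
- Restricted mean = (sum of reported times + 210 × number pain-free) ÷ 12, for complete sessions.

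**Worked set (assumed).** Without a dressing, 4 women report pain at 60 min, 4 at 180 min and 4 never. A dressing spares 4 of the 8 reporters and leaves the other times unchanged.

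| Condition | Reporter-only mean (min) | Restricted mean (min) |
|---|---|---|
| No dressing | (4×60 + 4×180)/8 = 120 | (4×60 + 4×180 + 4×210)/12 = 150 |
| Late reporters spared | (4×60)/4 = 60 | (4×60 + 8×210)/12 = 160 |
| Two of each spared | (2×60 + 2×180)/4 = 120 | (2×60 + 2×180 + 8×210)/12 = 180 |
| Early reporters spared | (4×180)/4 = 180 | (4×180 + 8×210)/12 = 200 |

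The differences from no dressing are −60, 0 and +60 min for the reporter-only mean, against +10, +30 and +50 min for the restricted mean. The same number of women is spared in each row, yet the reporter-only mean reverses, hides or overstates the benefit.

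**A smooth model (assumed).** Let S(t) = exp(−H(t/210)^k) with H = −ln(1−p), where p is the share of women in pain by 210 min without a dressing. With a hazard ratio of 0.5 the share with a dressing is q = 1 − (1−p)^0.5. The restricted mean r is the integral of S from 0 to 210, and the reporter-only mean is (r − 210(1−p))/p.

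For k = 1 and p = 0.50, q = 0.293. The restricted means are 151.5 and 177.5 min, a gain of 26.0. The reporter-only means are 93.0 and 98.9 min, a gap of 6.0 before rounding.

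| p | Reporter-only gap, k = 1 | Restricted gain, k = 1 | Share | Reporter-only gap, k = 4 | Restricted gain, k = 4 | Share |
|---|---|---|---|---|---|---|
| 0.25 | 2.5 | 13.1 | 0.19 | 1.4 | 5.4 | 0.25 |
| 0.50 | 6.0 | 26.0 | 0.23 | 3.3 | 11.0 | 0.30 |
| 0.75 | 11.5 | 37.9 | 0.30 | 6.6 | 17.1 | 0.39 |
| 0.90 | 17.4 | 42.6 | 0.41 | 10.7 | 21.1 | 0.51 |

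Over hazard ratios 0.3 to 0.7 and k from 0.5 to 4, the share runs from 0.14 to 0.55. Under proportional hazards, then, the usual effect is to shrink the difference.

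**Twelve women.** Simulation used k = 1, hazard ratio 0.5, p from 0.25 to 0.90 and within-woman correlation 0.3 to 0.7. It counted only runs with at least one reporter under both conditions. The reporter-only mean pointed the wrong way in 21% to 48% of runs, against 1% to 27% for the restricted mean. At p = 0.25 about 20% of runs had no reporter under one condition, and at p = 0.10 about 60% to 65%, so often no reporter-only comparison would exist. The highest wrong-sign rates occur where the reporter-only gap is only 2.5 min, which is close to a coin toss.

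**The case against.** The strongest reply is that the documents never say the field is left blank. Staff might enter 210 for every pain-free woman, and in complete sessions the mean is then exactly the restricted mean. This stands. A reader might infer that the plan commits to a biased mean, but the text supports only that the coding is unstated and that the literal reading gives a reporter-only mean.

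Second, the metric sentence in 5.2 speaks of time points, whereas time to pain has one value per session, so the fit is loose. Still, Table 3 labels the variable metric and the plan offers no other rule for it.

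Third, pain is also recorded as yes/no, and the last sentence of 5.2, on descriptive comparison, is not limited to metric variables. A reader might infer that pain counts will go unreported because 5.2 names numbers and proportions only for demographics. That goes too far, since some description of pain is likely. What remains is that no sentence requires counts beside the times or fixes a denominator. The counts matter: in the simulation at correlation 0.5, the count pointed the wrong way in about 2.5% to 12% of runs, ties not counted as wrong.

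Fourth, a reader might take the percentages above as the expected error in this trial, or conclude that a reporter-only mean always understates a benefit. Neither follows. The rates are assumed, healthy volunteers may report less pain than the range used, and the worked set shows overstatement and reversal as well.

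**Conclusion.** The concern holds as a gap in the definition and summary of one outcome. Table 3 and 5.2 do not say how a woman still pain-free at 210 minutes is counted, and applied literally they give a mean over reporters only, which can shrink, reverse or overstate a dressing difference.

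Its size in this trial cannot be stated. The distortion is absent if 210 is entered for pain-free women in complete sessions, or if every woman reports pain under every intervention.

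Priority is low, a change that could be made. The study is exploratory and descriptive, no outcome is primary, no error rate is at stake, and pain is captured in two other ways.

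**What to change.** In Table 3, define time to pain as minutes from the start of loading, censored at 210 minutes or at the actual end of loading if that is earlier.

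In 5.2, report for each intervention:
1. The number of women with pain out of those observed. This is the main safeguard.
2. The mean pain-free time restricted to 210 minutes, taken as the area under the Kaplan-Meier curve, in place of a plain mean of reported times. With complete sessions this equals entering 210 for pain-free women. A pain-free session that ends early enters as censored at its actual end, and is neither dropped nor given 210.

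The cost is one or two sentences and a minor extra analysis of data already collected. The actual end of loading must be noted for any session cut short. The restricted mean is only a lower bound on true pain-free time, because a woman still pain-free at the end counts for no more than 210 minutes. The table should say so.
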